6.0 Treatment of Subjects

6.1 Treatments Administered

This study will be conducted using the dosing schedule shown in Table 6-1. Projected doses are based on an 80 kg human. The dose has been selected based upon assumptions that the allometric scaling of terminal $t\frac{1}{2}$ will apply.

Table 6-1 Treatments

Cohort	Number of	Total Dose	Number of	Time of
	Subjects	(mg)	Doses	Dosing
	3	2	2; each divided	
I			among 8	Day 1, Day 15
			injection sites	
II	3	4	2; each divided	
			among 16	Day 1, Day 15
			injection sites	
III	3	8	2; each divided	
			among 16	Day 1, Day 15
		injection sites		
	3	16	2, each divided	
IV			among 16	Day 1, Day 15
			injection sites	

6.1.1 Treatment Regimen and Follow-Up

For each cohort, VM202 will be administered as either 8 or 16 local intramuscular injections to the affected limb in 2 divided doses with a 2-week interval between the injections. A total of 4 or 8 different injection sites will be arbitrarily chosen dependent on the dose and the location of the occluded vessels. The location of the injections sites will be documented on a leg diagram provided in the CRF. Each injection will contain a maximum of 2 ml (regardless of weight) and will be injected at each site slowly for about 20 to 30 seconds as described in Appendix D.

VM202 is provided in a sterile glass vial containing lyophilized 2.0 mg of study drug. Before use, it will be reconstituted with 4 ml of water for injection (WFI). Each reconstituted vial is only to be used for one patient. After the vial is reconstituted the following dosing information is applicable:

Cohort I has a total dose of 2.0 mg which is 1.0 mg per administration (0.25 mg per syringe in 0.5 ml for 4 injection sites per administration)

Cohort II has a total dose of 4.0 mg which is 2.0 mg per administration (0.25 mg per syringe in 0.5 ml for 8 injection sites per administration)

Cohort III has a total dose of 8.0 mg which is 4.0 mg per administration (0.5 mg per syringe in 1.0 ml for 8 injection sites per administration)

Cohort IV has a total dose of 16.0 mg which is 8.0 mg per administration (1.0 mg per syringe in 2.0 ml for 8 injection sites per administration)

VM202 will be administered in a 1.0 ml syringe for Cohorts I, II and III and a 3.0 ml syringe for Cohort IV. The volume of medication to be used for the four dose cohorts is as follows:

- Cohort I-fill 4 syringes with 0.5 ml per syringe
- Cohort II-fill 8 syringes with 0.5 ml per syringe
- Cohort III-fill 8 syringes with 1.0 ml per syringe
- Cohort IV-fill 8 syringes with 2.0 ml per syringe

The same volume will be used for both the first and the second doses (series of either 4 or 8 injections in only one affected leg) for each subject.

Injection volume by ml

Cohort	Dose	Volume/ administration	Volume/ injection site	Injections/Administration
I	1mg	2ml	0.5ml	4
II	2mg	4ml	0.5ml	8
III	4mg	8ml	1ml	8
IV	8mg	16ml	2ml	8

Injection volume by units

Cohort	Dose	Volume/ administration	Volume/ injection site	Injections/Administration
I	1mg	200units	50units	4
II	2mg	400units	50units	8
III	4mg	800units	100units	8
IV	8mg	1600units	200units	8

There will be a mandatory review of all safety data between the treatments of all dose cohorts (Cohorts I-IV). No subject may be enrolled in subsequent cohorts until the DSMC has reviewed the data and provided a written notice to the sponsor that the trial may continue.

In the event that a DLT is determined after the safety review in any cohort, there will be 3 additional subjects treated at the same dose level. If no further DLTs are observed in the 6 subjects and the DSMC approves dose escalation, then subjects can be enrolled to the

next higher dose level. If 2/6 subjects experience a DLT then the preceding dose level will be considered the MTD.

6.1.2 Study Agent Handling and Accountability

The vials will be labeled as required by all applicable regulations. The vials will be stored at 2-8°C. The vials (containing lyophilized VM202) may be kept up to 6 hours at room temperature prior to injection. If the vial is not used by 6 hours at room temperature, it must be discarded.

The vials of VM202 reconstituted with WFI may be kept up to 6 hours at room temperature prior to injection. If the vial is not used by 6 hours at room temperature, it must be discarded.

The study pharmacist will maintain accurate records of receipt of all test articles, including dates of receipt. In addition, accurate records will be kept regarding when and how much test article is administered to each individual subject in the study. Reasons for deviation from the expected regimen must also be recorded. An Investigational Drug Utilization Record will be provided for this purpose and will be signed by the study pharmacist at the conclusion of the study. At completion of the study in order to satisfy regulatory requirements regarding drug accountability and destruction, the study pharmacist will return all used, unused, empty, and partially used vials, with dispensing records, to the Sponsor for final accountability, inventory, and destruction.

6.2 Study Procedures and Study Procedures Chart

Study procedures to be performed are described by visit in the following sections and summarized in Table 4-1. Prior to performing any study-related procedures, the Principal Investigator (or his/her designated staff) will obtain written informed consent from the subject or the subject's legally authorized representative. After reading the informed consent document, the subject must give consent in writing. The subject's consent must be confirmed at the time of the subject's signature by the personally dated signature of the person conducting the informed consent discussions. The Investigator will retain the original signed consent document. A copy of the signed consent document will be given to the subject or the subject's legally authorized representative. "Legally authorized representative" means an individual or judicial or other body authorized under applicable law to consent on behalf of a prospective subject to the subject's participation in the procedure(s) involved in the clinical study. The Investigator will not undertake any measures specifically required for the clinical study until valid consent has been obtained.

6.2.1 Screening Visit (Day -30 to Day 1)

Subjects will be assessed for all inclusion/exclusion criteria. The screening visit may occur up to 30 days prior to the Day 1 visit. Data for any screening subject, regardless of

their eventual eligibility to participate in the study, will be documented in the study case report forms. The following procedures will be completed:

- Obtain written informed consent
- Medical history
- Chest X-ray or CT scan of the chest (if the subject has a previous history of tobacco use, a CT scan will be performed instead of the chest X-ray)
- Full physical examination including stool for occult blood
- Photograph and measurement of ulcer
- Vital signs
- Retinal fundoscopy
- Pregnancy test (female subjects only)
- Clinical laboratory tests, including: chemistry, hematology, urinalysis
- Tumor markers assessment
- Infection tests
- 12-lead electrocardiogram
- High resolution MRA
- Hemodynamic assessments (ABI and TBI)
- TcPO₂
- Assessment of all concomitant medications
- Pain VAS
- Analgesic use
- Mammogram/pap smear (for females) if not performed one year prior to study entry
- PSA (for males)
- CA-125 (for females)
- Endothelial progenitor cell assay

The subject will be screened for cancer and retinopathy to confirm that the patient is free of apparent neoplasms and proliferative retinopathy using any prior documentation of diagnostic tests and procedures performed prior to study consent and documented in the patient's medical history.

If the screening process is delayed and the assessments have fallen outside the screening period windows, then they must be repeated. If there are any questions regarding a subject's eligibility, please contact the Project Manager for clarification.

6.2.2 Day 1

Based on the subject meeting all of the screening procedures, the Investigator may administer the study agent to the patient following the Cohort assignment described above. If a subject is unable to receive the study agent because a clinically significant condition has evolved which, in the Investigator's opinion, represents a potential safety risk, the study drug will not be reassigned and the patient will be considered a screen failure. Therefore, it is important to determine the patient's medical status prior to the Day 1 visit and delay assignment until the condition resolves.

The following evaluations will be performed prior to study drug administration:

- Review all prior evaluations and confirm that subject meets all entry criteria
- Vital signs
- Digital photography and measurement of ulcer (if present)
- Clinical laboratory tests (chemistry, hematology, and urinalysis)
- Serum HGF
- Anti-HGF antibody level
- VM202 DNA level
- Hemodynamic assessments (ABI, TBI, Wave Form)
- TcPO₂
- Pain VAS
- Analgesic use
- Concomitant medications
- Adverse Events

If the subject meets all eligibility criteria, the following will be performed:

- Obtain study drug from the pharmacy
- Administer study drug in 8 separate injections as described above

After study drug administration, the subject will remain in a comfortable, supine position for observation for at least 60 minutes prior to being discharged. Any adverse reaction occurring during this period will be documented on the CRF.

Following study drug administration, the following evaluations will be performed:

- Vital signs (immediately after study drug administration and at 15, 30, and 60 minutes post-dose)
- Endothelial progenitor cell assay
- Concomitant medications
- Injection site reaction assessment

Adverse events

The subject is instructed to call the Study Coordinator if any of the following occur after discharge from the clinic:

- Hives
- Fever
- Rash
- Difficulty breathing
- Itching
- Worsening of a leg ulcer
- Redness or flushing at the site of the test dose

If any of the above occurs, the subject will be instructed to call the clinic immediately and seek medical attention either at the clinic or to go to the nearest Emergency Room for immediate treatment and evaluation. No further study drug administration will occur until it is determined if this is a DLT or as directed by the treating physician.

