Title: A Phase I, Dose-Escalation Study to Assess the Safety and

Tolerability of VM202 in Subjects with Critical Limb Ischemia

Study Phase: I

Treatment Duration: Study drug administered on two separate occasions, Days 1 and

15. Each treatment is divided into 4 or 8 IM injections.

Study Duration: 30 months

Individual Subject

Enrollment: 12 months

Name of Drug: VM202

Dosage: Cohort I-VM202 2 mg with the first half of the total dose given

on Day 1 and the second half given on Day 15

Cohort II-VM202 4 mg with the first half of the total dose given

on Day 1 and the second half given on Day 15

Cohort III-VM202 8 mg with the first half of the total dose

given on Day 1 and the second half given on Day 15

Cohort IV-VM202 16 mg with the first half of the total dose

given on Day 1 and the second half given on Day 15

Route of Administration: Intramuscular (IM) injection into the muscle closest to the

affected area. Volume determined by dose.

Study Objectives: To evaluate VM202 administered by intramuscular injection in

subjects with critical limb ischemia for the following:

1. Safety

2. Tolerability

3. Preliminary efficacy

Study Design: This is a prospective, dose-escalation study to evaluate the safety

and tolerability of intramuscular VM202 in subjects with critical

limb ischemia.

The study will consist of four (4) cohorts with a total of 3 subjects enrolled in each cohort to VM202. For each dose cohort, VM202 will be administered as a local intramuscular

injection in 2 divided doses with a 2-week interval between the injections. Preliminary efficacy (hemodynamic assessments), safety and tolerability will be evaluated at Baseline (screening) and at designated time points throughout the study.

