This Phase I study is designed to determine the safety and tolerability of intramuscular injections of VM202 using standard objective and subjective measurements. Assessment of safety will be accomplished through monitoring vital signs, monitoring signs and symptoms of acute and chronic hypersensitivity reaction and evaluating all observed and reported adverse events, retinal fundoscopy, clinical laboratory results, tumor lab testing, infection testing and urinalysis. There will also be a long-term follow-up to determine the extent of new onset of malignancy in treated subjects. CA-125 will be done in females and a PSA will be done in males to rule out any occult malignancy prior to first study drug administration and throughout the study.

While the primary objectives are safety and tolerability, preliminary efficacy evaluations will include evaluation of changes from Baseline in hemodynamics (ABI, TBI, Wave Form), TcPO₂, VAS pain assessment, analgesic use, and MRA measurements.

Procedures:

After the study subject is identified, a written informed consent will be obtained and screening process will be initiated. Hemodynamic assessments, TcPO₂, retinal fundoscopy and high resolution MRA will be done at Baseline. For subjects with

ischemic ulcer, a photograph and measurement of the ulcer will be obtained. Safety laboratory (hematology, chemistry, urinalysis), tumor marker tests, infection tests, chest X-ray or CT scan of the chest (if the subject has a previous history of tobacco use, a CT scan will be performed instead of the chest X-ray), and ECG will also be done at Baseline.

Subjects will be administered two doses of study drug on Days 1 and 15 as a local intra-muscular injection in the affected ischemic limb. There will be 4 or 8 injections depending on the dose level administered slowly for 20~30 seconds at predetermined sites on only one affected leg (mainly at the calf muscles) without local anesthesia. After treatment administration, subjects will be observed for 1 hour in a comfortable supine position.

Analgesic usage and Serum HGF will be assessed on Day 8 post first dose treatment.

After the second dose is administered (Day15) to the leg previously injected, hemodynamic assessments (ABI, TBI, Wave Form Analysis), TcPO₂, photograph and measurement of ischemic ulcer, VAS for pain, and safety labs will also be assessed on Days 28, 59, 91, 180 and 365. High resolution MRA with flow assessment will be done at Days 91 and 180.

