6.2.4 Day 15 (± 3 days) Second Study Dose Administration

The second dose of study drug will be administered at Day 15 (\pm 3 days). Prior to the administration of the study agent, the following will be performed:

- Physical exam
- Vital signs (immediately after study drug administration and at 15, 30, and 60 minutes post-dose)
- Photograph and measurement of ulcer
- Urine Pregnancy test (females of childbearing potential)
- Clinical laboratory tests
- Tumor markers
- Serum HGF level

- anti-HGF antibodies
- TcPO₂
- Hemodynamic assessment
- Pain VAS
- Analgesic use
- Concomitant medications
- Adverse events

The study drug will be administered in the same manner and in the same dose as performed on Day 1. Following study drug administration, the following evaluations will be performed:

- Vital signs
- Injection site reaction assessment
- Endothelial progenitor cell assay
- Adverse events
- 6.2.5 Day 16 (post 2nd dosing)

The following procedures will be performed at the Day 16 visit:

- Vital signs
- Adverse events
- Clinical laboratory tests
- Analgesic use
- Injection site reaction assessment
- Concomitant medications
- 6.2.6 Day 21 (\pm 3 days)

The following procedures will be performed at the Day 21 (+ 3 days) visit

- Vital signs
- Serum HGF
- VM202 DNA levels
- Injection site reaction assessment
- Analgesic use
- Concomitant medications
- Adverse events
- 6.2.7 Day 28 (\pm 3 days)

The following evaluations will be performed at Day 28 (\pm 3 days):

- Physical exam
- Vital signs
- Photograph and measurement of ulcer
- Clinical laboratory tests
- Hemodynamic assessments (ABI, TBI, Wave Form)
- Pain VAS
- TcPO₂
- Endothelial progenitor cell assay
- Analgesic use
- Injection site reaction assessment
- Concomitant medications
- Adverse events

After all subjects in Cohort I have completed the Day 28 visit, enrollment will be temporarily suspended until the DSMC has reviewed all of the safety data for all subjects. If the DSMC recommends that the trial continue, enrollment in Cohort II will commence and all of the procedures from Day -30 through Day 28 will be repeated for Cohort II.

After all subjects in Cohort II have completed the Day 28 visit, enrollment will be temporarily suspended until the DSMC has reviewed all of the safety data for all subjects. If the DSMC recommends that the trial continue, enrollment in Cohort III will commence and all of the procedures from Day -30 through Day 28 will be repeated for Cohort III.

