Appendix D

VM202 Test Material Preparation and Administration

1. Selection of injection sites

Identify occluded sites using contrast magnetic resonance (MRA) or computerized tomography (CTA) angiography. Select injection sites with the objective of inducing the formation of bridging collaterals from areas with normal blood flow and improving runin. Therefore, areas adjacent to the occluded sites and areas where blood flow through good collateral blood vessels decreases are desirable as injection sites. Documentation of injections sites will be indicated by placing an **X** on the diagram provided in the CRF and shown below.

2. Test material administration

On Day 1 and Day 15 the subject will receive test material. The study treatment will be administered as up to 8 injections. A fine needle (e.g. 27 gauge, 1") suitable for IM injections will be used; 2.0 ml will be administered per injection site (total volume of 8 or 16 ml per administration, determined by cohort assignment). Inject the entire amount of the drug in about 20-30 seconds. Immediately after completion of injection, lightly press the injection site with the finger head in order to prevent reflux. Do not massage the injection site.

3. Second test material administration

Each administration will be given at least 2 cm from the previous injection site. It is recommended that an indelible marker be used to mark the location of previous injections to ensure that repeat injections are not delivered to exact same location with the subsequent administration.

Injection Documentation Diagram

Indicate on drawing by marking an X at each injection site

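### Section 6.2.2 (Cohort I) and Table 6-1 (all cohorts) give twice the intended number of injections per administration, which at the stated dose halves the amount per site

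*Protocol*

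**What the plan says.** The Protocol states the number of injections in several places, and they do not agree.

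- **Section 6.1.1** gives the count per administration by cohort in the dosing text, the syringe fill list and both volume tables. Cohort I receives "0.25 mg per syringe in 0.5 ml for 4 injection sites per administration", and the fill list says "Cohort I-fill 4 syringes with 0.5 ml per syringe". Cohorts II-IV receive 8. The opening sentence counts over both days: "VM202 will be administered as either 8 or 16 local intramuscular injections to the affected limb in 2 divided doses".
- **Synopsis**: "Each treatment is divided into 4 or 8 IM injections" (Treatment Duration) and "There will be 4 or 8 injections" (Procedures), depending on dose level.
- **Appendix D**: "The study treatment will be administered as up to 8 injections".
- **Section 6.2.2 (Day 1)**: "Administer study drug in 8 separate injections as described above", for every cohort.
- **Section 6.2.4 (Day 15)**: "The study drug will be administered in the same manner and in the same dose as performed on Day 1".
- **Table 6-1**, which Section 6.1 names as the dosing schedule for the study, lists two doses, each divided among 8 injection sites in Cohort I and 16 in Cohorts II-IV.

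**The concern.** Section 6.2.2 is right for Cohorts II-IV and wrong for Cohort I. Because Section 6.2.4 repeats the Day 1 manner of administration, the error carries to the second dose. Table 6-1 is wrong for all four cohorts: its numbers match the two-day totals in Section 6.1.1, but the word *each* turns them into per-dose counts. The cross-reference in the Section 6.2.2 bullet does not settle the matter, because the text above it includes both Section 6.1.1 and Table 6-1.

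The amount and volume delivered at one site matter for two safety measures. Injection-site reaction is a primary safety endpoint (Section 4.1.1), and active tissue necrosis at the injection site is one of the three DLT criteria (Section 7.1.9). If the dose is spread over twice the planned number of sites, the cohort keeps its dose label while the local load is half of what was meant to be tested.

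The planned tables would not reveal this. SAP Section 10.1 and Table 11 summarize whether the dose was given, the injection zone, and whether total volume was per protocol. The number of injections is not tabulated, and twice as many half-volume injections would still count as the full volume.

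**Working it through.** **Inputs (Protocol Section 6.1.1 and Table 6-1)**

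- Vial: 2.0 mg reconstituted in 4 ml, so the concentration is 2.0 / 4 = 0.5 mg/ml.
- Total dose: 2/4/8/16 mg for Cohorts I-IV, given in two equal administrations, so 1/2/4/8 mg each.
- Volume per administration = dose / 0.5 = 2/4/8/16 ml, as in the Section 6.1.1 volume table.

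**Step 1. Reproduce the Section 6.1.1 figures with 4/8/8/8 sites.** Amount per site = dose per administration / number of sites; volume per site = volume per administration / number of sites.

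| Cohort | mg per site | ml per site | Check: sites × mg |
|---|---|---|---|
| I | 1/4 = 0.25 | 2/4 = 0.5 | 4 × 0.25 = 1 |
| II | 2/8 = 0.25 | 4/8 = 0.5 | 8 × 0.25 = 2 |
| III | 4/8 = 0.5 | 8/8 = 1.0 | 8 × 0.5 = 4 |
| IV | 8/8 = 1.0 | 16/8 = 2.0 | 8 × 1.0 = 8 |

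Every syringe amount and volume in Section 6.1.1 is reproduced exactly.

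**Step 2. Keep the stated dose and use the Table 6-1 count (8/16/16/16 per dose).**

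| Cohort | mg per site | ml per site | Ratio to Step 1 |
|---|---|---|---|
| I | 1/8 = 0.125 | 2/8 = 0.25 | 0.5 |
| II | 2/16 = 0.125 | 4/16 = 0.25 | 0.5 |
| III | 4/16 = 0.25 | 8/16 = 0.5 | 0.5 |
| IV | 8/16 = 0.5 | 16/16 = 1.0 | 0.5 |

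A Cohort IV site then receives what Section 6.1.1 plans for Cohort III, and a Cohort III site what it plans for Cohorts I and II.

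**Step 3. Keep the stated dose and use the Section 6.2.2 count (8 for all).** Cohort I: 1/8 = 0.125 mg in 2/8 = 0.25 ml, ratio 0.5. Cohorts II-IV are unchanged.

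**Step 4. Sites over both days.** Table 6-1 read literally needs 2 × 8 = 16 sites (Cohort I) or 2 × 16 = 32 (Cohorts II-IV) in one leg. Section 6.1.1 needs 2 × 4 = 8 or 2 × 8 = 16, which are the numbers printed in Table 6-1. This identifies the table's entries as two-day totals.

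**Step 5. Less likely case: keep the Section 6.1.1 syringe amount and use the wrong count.** Table 6-1 would give 8 × 0.25, 16 × 0.25, 16 × 0.5 and 16 × 1.0 = 2/4/8/16 mg per administration, or 4/8/16/32 mg in total, against that table's own total doses of 2/4/8/16 mg. Section 6.2.2 would give Cohort I 8 × 0.25 = 2 mg per administration instead of 1 mg.

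**The case against.** The strongest reply is that the working instruction is clear. Section 6.1.1 gives 4/8/8/8 in four forms, the pharmacist prepares the drug to detailed sponsor instructions (Section 4.4), and Cohort I drug arrives as four filled syringes, so giving eight injections would mean splitting them. The Table 6-1 numbers are correct as two-day totals and only mislabelled. The Section 6.2.2 error touches one cohort of three planned subjects at the lowest dose, where following it would lower the local load without changing the total dose. The loss of the top local load depends on Table 6-1 alone, since Section 6.2.2 is right for Cohort IV. Forward risk is also limited: the Version 5.0 amendment cites safety in the first two cohorts, so Cohort I was treated before then.

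Most of this stands as a limit on probability. It makes misdosing less likely, makes dose doubling the less likely of the two possible errors, and turns Cohorts I and II into a question of checking records. It does not remove the conflict, because Section 6.1 says the study is run from Table 6-1. The documents do not say when Cohorts III and IV were treated, and Version 5.0 opened the option of additional centers, whose staff could meet the conflicting counts for the first time.

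Appendix D is weaker support than it first appears. Its limit of 8 rules out 16 per administration, but it also states 2.0 ml per site, which fits only Cohort IV. The case for 4/8/8/8 therefore rests on the Section 6.1.1 arithmetic and the Synopsis, with Appendix D used only to exclude 16.

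**Conclusion.** The concern holds. The current text gives conflicting injection counts, and the intended count of 4/8/8/8 per administration can be established from the Protocol's own dose and volume figures. At the stated dose, the amount and volume per site are halved in all four cohorts under Table 6-1 and in Cohort I under Section 6.2.2. This rests on the total dose being kept as stated, which is the more likely way for staff to act on a wrong count. How likely either wrong count was to be used cannot be judged from the documents. It should be fixed: the error is in a dosing rule of a dose-escalation study and bears on a primary safety endpoint and a DLT criterion, although the detail in Section 6.1.1 makes actual harm less likely.

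**What to change.** - **Table 6-1**: state that each of the two doses is split over 4 sites in Cohort I and over 8 sites in Cohorts II-IV, with a note that this makes 8 or 16 injections across both days.
- **Section 6.2.2**: replace the fixed count of 8 with 4 injections for Cohort I and 8 for Cohorts II-IV, citing Section 6.1.1 by number. Section 6.2.4 then needs no change.
- **Subjects already treated**: check the CRF injection diagrams and the drug utilization records for the number of injections actually given on Days 1 and 15, and report any departure.

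The cost is a wording change to one table and one bullet, plus the records check. No procedures, visits or subjects are added.
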